5.3. Analysis of safety and reactogenicity

5.3.1. Analysis of safety and reactogenicity planned in the protocol

5.3.1.1. Within groups assessment

The safety will be descriptively summarized based on the ES. The analysis of local AEs, general AEs and fever will be reported for each RSV + comparator vaccine group and each active control comparator group and also for the pooled RSV vaccine and pooled comparator groups. For the analysis of SAEs and AE of specific interest, the analysis will be performed only on the pooled RSV and pooled comparator groups.

The percentage of subjects with at least one local AE (solicited and unsolicited), with at least one general AE (solicited and unsolicited) and with any AE during the 7-day or 30-day follow-up period will be tabulated with exact 95% confidence interval (CI) after each vaccine dose and overall. The percentage of doses followed by at least one local AE (solicited and unsolicited), by at least one general AE (solicited and unsolicited) and by any AE during the 7-day or 30-day follow-up period will be tabulated, overall vaccination course, with exact 95% CI. The same computations will be done for Grade 3 AEs, for any AEs considered related to vaccination for any Grade 3 AEs considered related to vaccination and AEs resulting in a medically attended visit.

The percentage of subjects reporting each individual solicited local AE (any grade, Grade 2, Grade 3, resulting in a medically attended visit) and solicited general AE (any grade, Grade 2, Grade 3, any related, Grade 2 related, Grade 3 related, resulting in medically attended visit) during the 7-day follow-up period (Day 1-7) will be tabulated for each

RSV + comparator vaccine group and each active control comparator group and also for the pooled RSV vaccine and pooled comparator groups after each vaccine dose and overall. Similarly, the percentage of doses followed by each individual solicited local and general AE and their sub-categories, will be tabulated, overall vaccination course, with exact 95% CI.

For fever, the number and percentage of subjects reporting fever by half degree (°C) cumulative increments during the 7-day follow-up period (Day 1-7) will be tabulated for each RSV + comparator vaccine group and each active control comparator group and also for the pooled RSV vaccine and pooled comparator groups after each vaccine dose and overall. Similar tabulations will be performed for any fever with a causal relationship to vaccination, Grade 3 ($> 40.0^{\circ}\text{C}$) causally related fever and for any fever resulting in a medically attended visit. In addition, the prevalence of any and Grade 3 fever will be presented graphically over time after vaccination.

For clinical safety laboratory parameters, a listing of laboratory value outside the normal range for the unscheduled visits will be provided as per the toxicity scale referred in the protocol. Laboratory values will be classified according to toxicity criteria (Table 7) of the SAP.

Laboratory values that are outside the normal range will also be flagged in the data listings, along with corresponding normal ranges and assessment of clinical significance

The percentage of subjects with unsolicited AEs within 30 days (Day 1-30) after each vaccine dose (overall doses) with its exact 95% CI will be tabulated RSV + comparator vaccine group and each active control comparator group and also for the pooled RSV vaccine and pooled comparator groups and by MedDRA preferred term. Similar tabulation will be done for Grade 3 unsolicited AEs, for any causally related unsolicited AEs, for Grade 3 causally related unsolicited AEs and for unsolicited AEs resulting in a medically attended visit. The verbatim reports of unsolicited AEs will be reviewed by a physician and the signs and AEs will be coded according to the MedDRA Dictionary for Adverse Reaction Terminology. Every verbatim term will be matched with the appropriate Preferred Term.

The percentage of subject with episode of spontaneous or excessive bleeding (AE of specific interest), during a 30-day follow-up period after each vaccination will be tabulated according to associated Preferred Term code mentioned in Section 9.4 of the SAP.

The percentage of subjects with RSV-LRTI (AE of specific interest) from Dose 1 up to end of the first RSV transmission season and from Dose 1 up to end of second RSV season will be tabulated according to associated Preferred Term code presented in the Section 9.4 of the SAP.

The percentage of subjects with SAE within 30 days (Day 1-30) after each vaccine dose with its exact 95% CI will be tabulated and by MedDRA preferred term. Similar tables will be generated for SAEs from Dose 1 to end of first RSV season and from Dose 1 to end of the second RSV season.

SAEs reported throughout the study and AE of special interest will be described in detail.

The percentage of subjects using concomitant medication (any medication, any antipyretic and any antipyretic taken prophylactically, respectively) during the 7-day follow-up period (Day 1-7) and during the 30-day follow-up period (Day 1-30) will be summarized by the pooled RSV vaccine and pooled comparator groups after each vaccine dose and overall.

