4. ANALYSIS SETS

4.1. Definition

4.1.1. Exposed Set

The Exposed Set (ES) will include all subjects with at least one study vaccine administration documented.

- A safety analysis based on the ES will include all vaccinated subjects.
- An immunogenicity analysis will be conducted on the ES and will include all vaccinated subjects for whom immunogenicity data are available.

The ES analysis will be performed per treatment actually administered at Dose 1

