5.3.2.3. Solicited Adverse Events

All analyses will be based on the ‘as treated’ analysis set. Solicited adverse events will be reported daily during the 7-day (from Day 1 to Day 7) follow up period after each vaccination, using structured diaries.

In order to summarize the data, the maximum intensity of local injection site redness/swelling (in mm) and fever (in $^{\circ}\text{C}$) will be categorized as follows:

Grading	Redness/swelling	Fever
0:	None	$< 38.0^{\circ}\text{C}$ (100.4°F)
1:	< 5 mm	$\geq 38.0^{\circ}\text{C}$ (100.4°F) - $\leq 39.0^{\circ}\text{C}$ (102.2°F)
2:	$> 5 - \leq 20$ mm	$> 39.0^{\circ}\text{C}$ (102.2°F) - $\leq 40.0^{\circ}\text{C}$ (104.0°F)
3:	> 20 mm	$> 40.0^{\circ}\text{C}$ (104.0°F)

Fever is defined as temperature $\geq 38.0^{\circ}\text{C} / 100.4^{\circ}\text{F}$ (regardless of the location of measurement). The preferred location for measuring temperature in this study will be the oral cavity. Body temperature will also be summarized by 0.5°C increments as follows: $\geq 38.0, >38.5, >39.0, >39.5, >40.0^{\circ}\text{C}$.

For each of the time points or time intervals presented in the summaries, only subjects with at least one plausible observation (i.e., any non-missing values but excluding “Not done/unknown” and implausible values) for the solicited adverse events in the interval of interest will be considered. Subjects without plausible data (i.e. missing values or reported as “Not done/unknown” and implausible values) will be removed from the denominator to prevent a downward bias (towards zero).

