Template 14 Compliance in completing solicited adverse events information <RSV 1D, RSV 2D, Comparator/Placebo> groups (Exposed Set)

		<Group 1>			<Group 2>				
		N	n	Compliance		N	n	Compliance	
				(%)				(%)	
<Vaccination at visit 1>	General solicited adverse events	xxx	xxx	xx.x	xxx	xxx	xxx	xx.x	
	Local solicited adverse events	xxx	xxx	xx.x	xxx	xxx	xxx	xx.x	
<Vaccination at visit X>	General solicited adverse events	xxx	xxx	xx.x	xxx	xxx	xxx	xx.x	
Per vaccination	Local solicited adverse events	xxx		xx.x	xxx	xxx	xxx	xx.x	
		xxx		xx.x	xxx	xxx	xxx	xx.x	
	General solicited adverse events	xxx	xxx						
	Local solicited adverse events								

Short group label = long group label

N=Number of administered vaccination

n = number of vaccination with Adverse Event Screen returned

Compliance (%) = (n / N) X 100

**Template 15 Summary of <grade 3> adverse events (solicited and unsolicited)
<with causal relationship to vaccination, with medically attend visit>
within <7, 30> days following first and second vaccination and
overall <RSV 1D, RSV 2D, Comparator/Placebo> <groups>< pooled
RSV 1D, RSV 2D, Comparator/Placebo groups> (Exposed Set)**

		<Each Group >			
				95% CI	
		n	%	LL	UL
<Vaccination at visit 1>	N	xxx			
	Any adverse event	xxx	xx.X	xx.X	xx.X
	Local adverse event	xxx	xx.X	xx.X	xx.X
	General adverse event	xxx	xx.X	xx.X	xx.X

<Vaccination at visit X>

Per subject

Per vaccination

Short group label = long group label

For each vaccination:

N = number of subjects with the corresponding administered vaccination

n/% = number/percentage of subjects presenting at least one type of adverse event following the corresponding dose

For per vaccination:

N = number of administered vaccination

n/% = number/percentage of vaccination followed by at least one type of adverse event

For per subject:

N = number of subjects with at least one administered vaccination

n/% = number/percentage of subjects presenting at least one type of adverse event

95% CI = Exact 95% confidence interval; LL = lower limit, UL = upper limit

Template 16 Percentage of subjects with solicited local adverse events by maximum intensity within the 7-day (Days 1-7) following first and second vaccination and overall - <RSV 1D, RSV 2D, Comparator/Placebo> <groups> < pooled RSV 1D, RSV 2D, Comparator/Placebo groups>(Exposed Set)

Adverse event: Pain

	<Group 1>				<Group 2>			
	n	%	95% CI		n	%	95% CI	
			LL	UL			LL	UL
<Vaccination at visit 1> N	XXX				XXX			

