Any	XXX	XX.X	XX.X	XX.X	XXX	XX.X	XX.X	XX.X
Grade 2	XXX	XX.X	XX.X	XX.X	XXX	XX.X	XX.X	XX.X
Grade 3	XXX	XX.X	XX.X	XX.X	XXX	XX.X	XX.X	XX.X
Medically attended visits								
<Vaccination at visit 3>								

Per subject

Per vaccination

Adverse event: Swelling/Redness

	<Group 1>				<Group 2>			
	n	%	95% CI		n	%	95% CI	
			LL	UL			LL	UL
<Vaccination at visit 1> N	XXX				XXX			
Any	XXX	XX.X	XX.X	XX.X	XXX	XX.X	XX.X	XX.X
≥5 - ≤ 20	XXX	XX.X	XX.X	XX.X	XXX	XX.X	XX.X	XX.X
>20	XXX	XX.X	XX.X	XX.X	XXX	XX.X	XX.X	XX.X
Medically attended visits								
<Vaccination at visit 3>								

Per subject

Per vaccination

<each group>:

For each vaccination:

N = number of subjects with the corresponding documented vaccination

n/% = number/percentage of subjects reporting the type of adverse event at least once following the corresponding vaccination

For Per vaccination:

N = number of documented vaccination

n/% = number/percentage of vaccination followed by at least one type of adverse event

For Per subject:

N = number of subjects with at least one documented vaccination

n/% = number/percentage of subjects reporting the type of adverse event at least once

95%CI= Exact 95% confidence interval; LL = lower limit, UL = upper limit

The maximum intensity of local injection site redness/swelling was coded as follows:

1: > 0.1 mm to < 5 mm

2: ≥ 5 mm to ≤ 20 mm

3: > 20 mm

Please note – The N may vary for each symptom depending on how many subjects has filled in diary card for particular symptom.

Template 17 Duration in days of solicited <general, local> adverse events within 7 days following first and second vaccination and overall <RSV 1D, RSV 2D, Comparator/Placebo> groups (Exposed Set)

	Symptom	<Group 1> Value	<Group 2> Value
<Vaccination at visit 1>	<Symptom 1>		
	n	xxx	xxx
	Mean	xxx.x	xxx.x
	Minimum	xxx	xxx
	Q1	xxx.x	xxx.x
	Median	xxx.x	xxx.x
	Q3	xxx.x	xxx.x
	Maximum	xxx	xxx
	<Symptom 2>		

<Vaccination at visit X>

Per vaccination

Short group label = long group label

n = number of doses with the adverse event

Q1 = 25th percentile

Q3 = 75th percentile

Template 18 Percentage of subjects with solicited general adverse events by maximum intensity within the 7-day (Days 1-7) following first and second vaccination and overall - <RSV 1D, RSV 2D, Comparator/Placebo> <groups> < pooled RSV 1D, RSV 2D, Comparator/Placebo groups >(Exposed Set)

Adverse event: Irritability/Fussiness or Drowsiness or Loss of appetite

	<Group 1>				<Group 2>			
			95% CI				95% CI	

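### The combined solicited-plus-unsolicited AE tables count infants without solicited data as free of solicited reactions, a bias the SAP prevents only in its solicited-only tables

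*SAP*

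**What the plan says.** Section 5.3.1.1 of the SAP opens with "The safety will be descriptively summarized based on the ES", and section 4.1.1 adds that "A safety analysis based on the ES will include all vaccinated subjects". On that set it plans "The percentage of subjects with at least one local AE (solicited and unsolicited), with at least one general AE (solicited and unsolicited"), plus the rate for any AE, after each dose and overall. The computations are repeated for Grade 3, related, Grade 3 related and medically attended events. The sentence itself names no denominator.

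The denominators are in the mock tables (section 13):

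- **Template 15**, which presents these combined rates, uses for each dose "N = number of subjects with the corresponding administered vaccination", for the per-subject rows "N = number of subjects with at least one administered vaccination", and for the per-vaccination rows all administered vaccinations.
- **Template 29**, the combined table by system organ class and preferred term with SAEs excluded, uses the same per-subject N.

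Solicited-only summaries follow another rule. Under section 5.3.2.3, subjects without plausible solicited data "will be removed from the denominator to prevent a downward bias (towards zero"). Section 10.1.2.3.1 limits the denominator to subjects who answered the occurrence question either way. Templates 16 and 18 define "N = number of subjects with the corresponding documented vaccination" and add a note that N may differ by event according to diary completion. Template 15 has no such note. Template 14 reports diary compliance, with "N=Number of administered vaccination" as its base, but no table uses it to adjust a rate.

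**The concern.** Solicited reactions are collected in diaries over Days 1 to 7. If an infant's solicited data are missing, the combined tables keep the infant in the denominator, and the infant can reach the numerator only through an unsolicited AE or an SAE. Missing solicited data are thus treated as observed absence of a reaction, and the exact confidence interval takes this as information.

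The SAP recognises this bias and removes it symptom by symptom, then leaves it in the summary that pools the same symptoms. The error runs towards understating reactogenicity. The tables can also contradict each other: a rate for any local AE can be smaller than the rate for pain alone.

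Section 5.3.1.2 raises a related question. Its Day 1-7 group differences cover Grade 2/3 AEs and fever above 39.0°C, which depend largely on diary data, yet it states no denominator and no mock table shows these differences.

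**Working it through.** **Inputs.** The SAP gives no expected AE rate and no diary return rate for this point, so there is no stated figure to reproduce. The target is 50 infants per pooled group (Table 2). The remaining inputs are assumptions:

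- p: share of infants with a solicited event
- q: share with an unsolicited AE, independent of solicited events
- u: share with no solicited data, taken to have the same p and q as the others

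**Formula.**

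- Any-AE rate with complete data: p + q − pq
- Rate under Template 15: (1 − u)(p + q − pq) + uq
- Shortfall: u × p × (1 − q), which is largest at q = 0, where it equals u × p

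**Worked case**, p = 60%, q = 30%, u = 10%: complete-data rate 0.60 + 0.30 − 0.18 = 72.0%; Template 15 rate 0.90 × 0.72 + 0.10 × 0.30 = 67.8%; shortfall 4.2 points.

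**Range at p = 60%** (percentage points):

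| u | q = 0 (upper bound) | q = 30% |
|---|---|---|
| 2% | 1.2 | 0.8 |
| 6% | 3.6 | 2.5 |
| 10% | 6.0 | 4.2 |
| 20% | 12.0 | 8.4 |

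**Coherence between tables.** Take 50 vaccinated infants, 45 with solicited data, 27 of them with pain, and no other local event in the group.

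- Template 16, pain: 27/45 = 60.0% (exact 95% CI 44.3 to 74.3)
- Template 15, any local AE: 27/50 = 54.0% (39.3 to 68.2)

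The union comes out rarer than one of its components. With one diary missing the gap is small: 29/49 = 59.2% against 29/50 = 58.0%.

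**Group differences, if the all-vaccinated N were used in 5.3.1.2.** With equal u in both groups and q = 0, a true difference shrinks by the factor 1 − u: 20 points becomes 19.6 at u = 2% and 18.0 at u = 10%. With unequal u, an artefact appears. For true rates of 50% in both groups and u of 12% against 4%, it is 0.50 × 0.88 − 0.50 × 0.96 = −4 points. The approximate 95% half-width for such a difference is 1.96 × √(2 × 0.5 × 0.5 / 50) = 0.196, or about 20 points.

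**The case against.** The case for the plan as written has real force.

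- **No explicit rule is broken.** A reader might infer that Template 15 violates section 5.3.2.3. It does not: that section covers solicited AEs and says nothing about combined tables. The inconsistency is one of principle.
- **All vaccinated infants is a defensible N.** It is the declared safety population. The combined endpoint includes unsolicited AEs, and section 10.1.3.12 counts SAEs as general events in combined output. Replacing this N outright would drop infants with a known AE or SAE because a diary is missing.
- **The administered-versus-documented wording proves little.** Section 4.1.1 defines the Exposed Set itself by documented administration. The link to diary data comes from sections 5.3.2.3 and 10.1.2.3.1 and from the notes under Templates 16 and 18.
- **The loss is partial.** Unsolicited AEs and SAEs in infants without a diary still count, so u × p is only an upper bound under the stated assumptions.
- **The combined rate is not an itemised primary endpoint.** Section 3.2.1 lists each solicited AE, unsolicited AEs, SAEs and bleeding episodes. Solicited AEs are reported with completion-dependent N in Templates 16 and 18, and Template 14 shows compliance by group.

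A reader might also infer that the RSV-minus-control differences are biased. The document does not establish this. Section 5.3.1.2 fixes no denominator, Epoch 002 is observer-blind, nothing suggests that diary return differs by group, and section 6 calls the comparisons exploratory.

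All these points stand, and they limit the finding. They do not answer the core of it: no section extends the missing-data rule to the combined tables or adds a version based on available solicited data.

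**Conclusion.** The concern holds in a limited form. Followed as written, Templates 15 and 29 score infants without solicited data as having no solicited reaction, so the solicited part of the combined rates is understated.

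With p = 60% and q = 30% the shortfall is under one point at 2% non-return and about four points at 10%. For the local rows it lies closer to u × p if unsolicited local events are uncommon, which the SAP neither states nor excludes. The figures rest on assumed rates, on independence of solicited and unsolicited events, and on infants without a diary resembling the rest. If those infants reacted more often, the shortfall would be larger.

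At 50 infants per pooled group these amounts are small beside the confidence intervals, but they are systematic and can make related tables disagree. This is a low to moderate priority correction, not an invalid safety analysis.

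**What to change.** 1. **Template 15:** keep the all-vaccinated rows. Add rows for the 7-day local, general and any-AE rates with N equal to the infants (or doses) with solicited data for the period, and say that reactogenicity is to be read from these rows.
2. **Template 29:** state in a footnote that N includes infants without solicited data.
3. **Section 5.3.1.2:** state the denominator. Give the Day 1-7 Grade 2/3 AE and fever above 39.0°C differences on infants with solicited data as well as on all vaccinated infants.
4. **Templates 21, 30 and 56:** leave unchanged, since all vaccinated infants is the right base for unsolicited AEs and SAEs.

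The cost is footnote wording and a few extra rows. The added rows omit unsolicited events in infants without a diary, but those events remain in the all-vaccinated rows and in Templates 21 and 56.

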 - **Active surveillance:** parent(s)/LAR(s) of all the subjects will be contacted by the investigator/study staff on a regular basis (weekly during the RSV season and every month outside the RSV season) to identify any potential RSV-RTI and to remind the parent(s)/LAR(s) of the subjects to report any new occurrence of RTI symptoms (cough, runny nose or blocked nose), or in case of difficulty in breathing or wheezing as soon as possible.

Refer to Section 9.2 of the protocol for more information about active and passive surveillance.

- Surveillance for spontaneous or excessive bleeding - Subjects' parent(s)/LAR(s) will be instructed to contact the investigator/study staff if their child presents symptoms of spontaneous bleeding or easy bruising or if their child develops a rash, within 30 days after either vaccination (Visit 1 and Visit 3), in order to detect any thrombocytopenic petechiae or purpura. The investigator will, based on his/her medical judgment, measure the total blood count and appropriately investigate infants with clinical suspicion of low platelets.
- **Group description:** - For the blinded report on safety/reactogenicity, the analyses will be presented as one group (RSV groups and Placebo group being pooled).

The following group names for the unblinded analysis will be used in the TFLs, to be in line with the T-domains:

Group order in tables	Group label in tables	Group definition for footnote	Pooled Groups label in tables – UNBLINDED ANALYSIS	Pooled definition for footnote - UNBLINDED ANALYSIS
1	RSVBEX1D	RSV 1D + BEXERO 3D	RSV 1D	Pooled 1D RSV
2	RSVNIM1D	RSV 1D +NIMENRIX 3D		
3	RSVSYN1D	RSV 1D +SYNFLORIX 3D		
4	RSVMEN1D	RSV 1D +MENVEO 2D		
5	RSVPBO1D	RSV 1D + PLACEBO		
6	RSVBEX2D	RSV 2D + BEXERO 3D	RSV 2D	Pooled 2D RSV
7	RSVNIM2D	RSV 2D +NIMENRIX 3D		
8	RSVSYN2D	RSV 2D +SYNFLORIX 3D		
9	RSVMEN2D	RSV 2D +MENVEO 2D		
10	RSVPBO2D	RSV 2D + PLACEBO		
11	BEXERO	BEXERO 3D	COMP_PLB	Pooled comparator
12	NIMENRIX	NIMENRIX 3D		
13	SYNFLORIX	SYNFLORIX 3D		
14	MENVEO	MENVEO 2D		
15	PLACEBO	PLACEBO		

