3.2. Endpoints

3.2.1. Primary endpoints

- Occurrence of adverse events (AEs) from first vaccination (Day 1) up to Day 61
 - Occurrence of each solicited local and general AE, during a 7-day follow-up period after each vaccination (i.e., the day of vaccination and 6 subsequent days)
 - Occurrence of any unsolicited AE, during a 30-day follow-up period after each vaccination (i.e., the day of vaccination and 29 subsequent days)
 - Occurrence of any serious adverse event (SAE) from Day 1 up to Day 61
 - Occurrence of episode of spontaneous or excessive bleeding (AE of special interest), during a 30-day follow-up period after each vaccination

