9.4. Coding for the AE of specific interest

Any of the below listed preferred term reported as an Expedited Adverse Event must be immediately escalated to the CRDL or Central Safety Physician to assess or confirm the need for an urgent IDMC review.

The list of preferred terms and associated PT codes is given below:

HAEMATOMA

Preferred term	PT code
abdominal wall haematoma	10067383
administration site haematoma	10075100
adrenal haematoma	10059194
aortic intramural haematoma	10067975
application site haematoma	10068317
arterial intramural haematoma	10074971
auricular haematoma	10003797
basal ganglia haematoma	10077031
brain stem haematoma	10073230
breast haematoma	10064753
broad ligament haematoma	10006375
bursal haematoma	10077818
catheter site haematoma	10055662
cephalhaematoma	10008014
cerebellar haematoma	10061038
cerebral haematoma	10053942
cervix haematoma uterine	10050020
chest wall haematoma	10076597
colonic haematoma	10009996
deep dissecting haematoma	10074718
extradural haematoma	10015769
eyelid haematoma	10064976
haematoma	10018852
haematoma evacuation	10060733
haematoma infection	10051564
hepatic haematoma	10019676
incision site haematoma	10059241
infusion site haematoma	10065463
injection site haematoma	10022066
instillation site haematoma	10073609
intestinal haematoma	10069829
intra-abdominal haematoma	10056457
intracerebral haematoma evacuation	10062025

Preferred term	PT code
intracranial haematoma	10059491
intraocular haematoma	10071934
laryngeal haematoma	10070885
lip haematoma	10066304
mediastinal haematoma	10049941
medical device site haematoma	10075577
mesenteric haematoma	10071557
nasal septum haematoma	10075027
oesophageal intramural haematoma	10077486
oral mucosa haematoma	10074779
ovarian haematoma	10033263
paranasal sinus haematoma	10069702
pelvic haematoma	10054974
penile haematoma	10070656
perineal haematoma	10034520
periorbital haematoma	10034544
periosteal haematoma	10077341
perirenal haematoma	10049450
peritoneal haematoma	10058095
pharyngeal haematoma	10068121
post procedural haematoma	10063188
pulmonary haematoma	10054991
renal haematoma	10038459
retroperitoneal haematoma	10058360
scrotal haematoma	10039749
spinal cord haematoma	10076051
spinal epidural haematoma	10050162
spinal subdural haematoma	10050164
splenic haematoma	10041646
spontaneous haematoma	10065304
subarachnoid haematoma	10076701
subcutaneous haematoma	10042345
subdural haematoma	10042361
subgaleal haematoma	10069510
subretinal haematoma	10071935

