mucocutaneous haemorrhage	10076048
mucosal haemorrhage	10061298
muscle haemorrhage	10028309
myocardial haemorrhage	10048849
naevus haemorrhage	10062955
ocular retrobulbar haemorrhage	10057571
oesophageal haemorrhage	10030172
optic disc haemorrhage	10030919
optic nerve sheath haemorrhage	10030941
ovarian haemorrhage	10065741
pancreatic haemorrhage	10033625
papillary muscle haemorrhage	10059164
parathyroid haemorrhage	10059051

Preferred term	PT code
parotid gland haemorrhage	10051166
pelvic haemorrhage	10063678
penile haemorrhage	10034305
pericardial haemorrhage	10034476
periorbital haemorrhage	10071697
peritoneal haemorrhage	10034666
Petechiae	10034754
pharyngeal haemorrhage	10034827
pituitary haemorrhage	10049760
post procedural haemorrhage	10051077
procedural haemorrhage	10071229
prostatic haemorrhage	10036960
pulmonary alveolar haemorrhage	10037313
pulmonary haemorrhage	10037394
putamen haemorrhage	10058940
rectal haemorrhage	10038063
renal haemorrhage	10038460
respiratory tract haemorrhage	10038727
retinal haemorrhage	10038867
retroperitoneal haemorrhage	10038980
scleral haemorrhage	10050508
skin haemorrhage	10064265
small intestinal haemorrhage	10052535
soft tissue haemorrhage	10051297
spermatic cord haemorrhage	10065742
spinal cord haemorrhage	10048992
spinal epidural haemorrhage	10049236
spinal subarachnoid haemorrhage	10073564
spinal subdural haemorrhage	10073563
splenic haemorrhage	10041647
spontaneous haemorrhage	10074557
subarachnoid haemorrhage	10042316
subdural haemorrhage	10042364
testicular haemorrhage	10051877
thalamus haemorrhage	10058939
thoracic haemorrhage	10062744
thyroid haemorrhage	10064224
tongue haemorrhage	10049870
tracheal haemorrhage	10062543
upper gastrointestinal haemorrhage	10046274
ureteric haemorrhage	10065743

Preferred term	PT code
urethral haemorrhage	10049710
urinary bladder haemorrhage	10046528
urogenital haemorrhage	10050058
uterine haemorrhage	10046788
vaccination site haemorrhage	10069475
vaginal haemorrhage	10046910
venous haemorrhage	10065441
vitreous haemorrhage	10047655
vulval haemorrhage	10063816

THROMBOCYTOPENIA

Preferred term	PT code
bleeding time abnormal	10049227
bleeding time prolonged	10005140
coagulation test abnormal	10063557
platelet count abnormal	10035526
platelet count decreased	10035528
platelet disorder	10035532
platelet dysfunction	10073391
Thrombocytopenia	10043554
thrombocytopenic purpura	10043561

LOWER RESPIRATORY TRACT INFECTION

Preferred term	PT code
atypical pneumonia	10003757

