XX	XX		XX	XX	XX	XX			XX	XX		xx	Hemoglobin		
													Platelet count		
												xx	Hemoglobin		
													Platelet count		
													...		

<each group>:

*AEs related to spontaneous or excessive bleeding will be identified based on the list of preferred terms described in section 9.4 –Annex

AESI: AEs of Special Interest – Spontaneous or excessive bleeding identified by the Investigator

Template 26 Listing of adverse events, SAEs and solicited symptoms leading to study or treatment discontinuation from vaccination dose 1 up to <Day 61/end of first RSV season/end of second RSV season>(Exposed Set)

Type of discontinuation: <study/treatment>

Group	Subject number	Gender	Country	Race	AE Description	SAE (Y/N)	Causality	Outcome	Vaccination and visit
xxxxx	xxxxx	xxxxx	xxxxxxxx	xxxxxx	xxxxxx	x	xxxxx	xxxxx	Vaccination: x at visit x

Template 27 Listing of unscheduled safety visit from vaccination dose 1 up to <Day 61/end of first RSV season/study end> (Exposed Set)

Group	Sub.No.	Gender	Country	Race	Age at unscheduled visit (Month)	Date of previous safety BS	Date of unscheduled safety BS	Result of previous safety BS out of lab range	Grade of abnormality per protocol – previous safety BS	Result of biochemistry/ hematology at unscheduled visit	Outcome of unscheduled safety visit

<each group>:

Please note that only unscheduled safety visits with abnormal safety parameters will be presented.

Template 28 Summary of subjects taking a concomitant medication within <7/30> days following each vaccination and overall <RSV 1D, RSV 2D, Comparator/Placebo> <groups>< for pooled RSV 1D, RSV 2D and Comparator/Placebo groups> (Exposed Set)

	<Group 1>				<Group 2>			
			95% CI				95% CI	
	n	%	LL	UL	n	%	LL	UL
<Vaccination at visit 1> N	xxx				xxx			
Any	xxx	xx.x	xx.x	xx.x	xxx	xx.x	xx.x	xx.x
Any antipyretic	xxx	xx.x	xx.x	xx.x	xxx	xx.x	xx.x	xx.x
Any prophylactic antipyretic	xxx	xx.x	xx.x	xx.x	xxx	xx.x	xx.x	xx.x

<Vaccination at visit X>

Per subject

Per vaccination

Short group label = long group label

For each vaccination:

N = number of subjects with the corresponding administered vaccination

n/% = number/percentage of subjects who took the specified type of concomitant medication at least once during the considered period

For per vaccination:

N = number of administered vaccination

n/% = number/percentage of vaccines after which the specified type of concomitant medication was taken at least once during the considered period

For per subject:

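### The bleeding event of special interest, a primary endpoint, is selected by a term list that omits bruising, plain purpura and nosebleed terms but counts needle-site haematomas, and the investigator's own identification does not enter the selection

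*SAP*

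**What the plan says.** SAP section 3.2.1 lists among the primary endpoints: "Occurrence of episode of spontaneous or excessive bleeding (AE of special interest), during a 30-day follow-up period after each vaccination".

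Section 2 describes the surveillance behind it. Parents are to contact the site "if their child presents symptoms of spontaneous bleeding or easy bruising or if their child develops a rash", and the stated purpose is "in order to detect any thrombocytopenic petechiae or purpura". Whether to take a blood count is left to the investigator's judgment.

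For the analysis, section 5.3.1.1 says that the percentage "will be tabulated according to associated Preferred Term code mentioned in Section 9.4 of the SAP". The footnote to Template 25, the bleeding listing, says that "AEs related to spontaneous or excessive bleeding will be identified based on the list of preferred terms described in section 9.4". Template 25 also has a column showing whether the investigator identified the event as an AESI.

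Section 9.4 introduces its terms as an escalation list for expedited reports, then sets them out in four blocks: haematoma, haemorrhage, thrombocytopenia and lower respiratory tract infection. It does not say which blocks make up the bleeding AESI. The first three are the natural reading, because the only other AESI is RSV-LRTI.

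**The concern.** A list built to prompt escalation can afford to be broad. When the same list also fixes the numerator of a primary endpoint, its contents need to match what the endpoint is meant to count, and here they diverge in two directions. A symptom that parents are asked to report, easy bruising, has no term of its own, and purpura appears only in its thrombocytopenic form. Local bleeding at the needle site, which need not be either spontaneous or excessive, has several terms.

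The investigator's judgment that an event is a bleeding AESI is recorded, but only as a column beside rows that the list has already chosen. At stake is whether the reported percentage means what its label says, in a trial where one infant per group is visible in the estimate.

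**Working it through.** **Search of the list.** The section 9.4 blocks hold 74 haematoma terms, 131 haemorrhage terms and 9 thrombocytopenia terms: 74 + 131 + 9 = 214. A text search of these gives:

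| Sought | Found |
|---|---|
| bruising, contusion, ecchymosis | none |
| epistaxis or nose | none (the two nasal terms are nasal septum haematoma and paranasal sinus haematoma) |
| purpura | one, thrombocytopenic purpura |
| petechiae | one |
| terms containing *site* | 14 (9 haematoma, 5 haemorrhage), including injection, vaccination and administration site for both |
| procedural | 3 |
| pure test results | 5 (two bleeding time, two platelet count, one coagulation test) |

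**What the rules do with four kinds of event.** This applies sections 5.3.1.1 and 9.4 and Template 25 as written.

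1. Petechiae, thrombocytopenia or thrombocytopenic purpura: listed, so in the percentage and in Template 25.
2. An event the investigator identifies as a bleeding AESI but that is coded to a bruising, plain purpura or nosebleed term: not listed, so in neither. It remains in the 30-day unsolicited event tables by preferred term (Template 21) and in the individual listing of unsolicited events (Appendix Table II.Ci).
3. "injection site haematoma" or its vaccination-site counterpart: listed, so in the headline row whether or not the investigator regarded it as a bleeding AESI. The solicited local symptoms in section 5.3.2.1 are pain, redness and swelling, so a haematoma would be reported as unsolicited and reach this count.
4. A test-result term such as "coagulation test abnormal" or platelet count decreased: counted if the thrombocytopenia block belongs to the bleeding AESI, which section 9.4 leaves unstated.

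**Weight of one infant.** The SAP gives no rate or precision figure for this endpoint, so there is none to reproduce. Table 2 sets a target of 50 infants per pooled group, and 1/50 = 2 percentage points. With the Clopper-Pearson interval that the SAP specifies for proportions:

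| Infants counted | Rate | Exact 95% CI |
|---|---|---|
| 0/50 | 0% | 0 to 7.1% |
| 1/50 | 2.0% | 0.05 to 10.6% |
| 2/50 | 4.0% | 0.5 to 13.7% |
| 3/50 | 6.0% | 1.3 to 16.5% |

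One off-list case can thus turn 2% into 0%. Three needle-site haematomas with no other bleeding would show as 6%.

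**The case against.** Much can be said for the plan.

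The stated surveillance target is largely covered: petechiae, thrombocytopenia, thrombocytopenic purpura and decreased platelet count are all listed, as are subcutaneous haematoma, skin haemorrhage and mucocutaneous haemorrhage. Bruising and rash are prompts for a parent to call, not the endpoint itself. This stands, and it rules out any claim that the endpoint misses its core cases.

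The codes might also be meant only to classify episodes already identified as bleeding AESIs; the wording of Template 21 allows that. If so, a trivial needle-site haematoma would not count. That is a fair reading of section 5.3.1.1, but it does not fit the Template 25 footnote, where the list does the identifying. It also leaves no stated place for an identified episode whose code is off the list. The ambiguity is itself something to settle.

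Omitted events are not hidden. They stay in the general tables and listings, section 5.3.1.1 promises a detailed description of AESIs, and Template 21 gives each preferred term its own row, so a reader could separate needle-site events by hand. This limits the harm but does not repair the headline percentage.

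The endpoint is descriptive, and Table 1 has every group injected at Visits 1 and 3, so needle trauma is not confined to one arm. This also stands.

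Three stronger inferences are tempting and are not supported:

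- That a sizeable number of infants will be misclassified. The SAP gives no bruise rate and does not say how a verbatim bruise would be coded. If bruises were coded as haematoma, the under-count would shrink as the over-count grew, so one assumption cannot support both.
- That off-list events would escape urgent review. Section 9.4 says that listed expedited terms must be escalated. It does not say that others are not, and Figure 1 describes monthly committee review of accumulating safety data.
- That all laboratory terms should leave the AESI. Low platelets are a signal that the surveillance is looking for.

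**Conclusion.** The point holds as a mismatch between the rule that selects the endpoint and the surveillance that feeds it. As written, the list alone decides what enters the bleeding percentage and Template 25. It lacks terms for a symptom that the surveillance names and for purpura not coded as thrombocytopenic. It admits needle-site haematomas and haemorrhages to the headline row.

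The size is 2 percentage points per affected infant at 50 per pooled group; the number affected cannot be derived from the document. The conclusion assumes the plain reading of section 5.3.1.1 (the list selects) and that the haematoma, haemorrhage and thrombocytopenia blocks together form the bleeding AESI. It is worth correcting because this is a primary endpoint and the change is cheap, but it does not show that the core cases of thrombocytopenic bleeding would be lost.

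**What to change.** Amend sections 5.3.1.1 and 9.4 and the Template 25 footnote as follows:

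- Define the bleeding AESI, for both the percentage and the Template 25 selection, as an event that the investigator identified as a bleeding AESI or that carries a listed term.
- Add bruising/contusion, ecchymosis, purpura and epistaxis terms.
- State that the haematoma, haemorrhage and thrombocytopenia blocks make up the bleeding AESI.
- Show injection-, vaccination- and administration-site terms and procedural terms on a separate row outside the headline percentage, unless the investigator identified the event as an AESI.
- Keep platelet and thrombocytopenia terms in the AESI output as a distinct subcategory.

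The cost is a revised term list and one derivation. The case count becomes slightly broader. The investigator's identification already has a column in Template 25, so no new data are needed.
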